7.6.3 Vital Signs

Each vital sign (temperature, blood pressure (systolic and diastolic), respiration rate, and heart rate) at baseline will be summarized and presented by treatment group. The number and percentage of subjects with marked abnormalities in vital signs as compared to baseline will be summarized and listed.

Parameter	Criteria for Marked Abnormality
Systolic Blood Pressure	Absolute result > 160 mmHg and increase from baseline > 20 mmHg
	Absolute result < 90 mmHg and decrease from baseline > 20 mmHg
Diastolic Blood Pressure	Absolute result > 100 mmHg and increase from baseline > 10 mmHg
	Absolute result < 50 mmHg and decrease from baseline > 10 mmHg
Heart Rate	Absolute result > 100 bpm and increase from baseline > 30 bpm
	Absolute result < 60 bpm and decrease from baseline > 20 bpm

Data will be summarized and presented according to the following categories:

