- Any prior malignancy (other than adequately treated basal cell or squamous cell skin cancer, superficial bladder cancer, or any other cancer in situ currently in complete remission) within 5 years prior to randomization
  - Any of the following within 6 months prior to randomization: Severe/unstable angina, myocardial infarction, symptomatic congestive heart failure, arterial or venous thromboembolic events (e.g., pulmonary embolism, cerebrovascular accident including transient ischemic attacks), or clinically significant ventricular arrhythmias
  - Uncontrolled hypertension (systolic blood pressure  $\geq 160$  mmHg or diastolic BP  $\geq 100$  mmHg). Patients with a history of uncontrolled hypertension are allowed provided blood pressure is controlled by anti-hypertensive treatment.
  - Gastrointestinal disorder affecting absorption
  - Active infection, such as human immunodeficiency virus (HIV)
  - Any other condition that, in the opinion of the Investigator, would impair the patient's ability to comply with study procedures.

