#### **7.1.4 Vital Signs**

Body temperature, blood pressure, pulse and respiratory rate will be performed after resting for 5 minutes at Screening and every scheduled visit during treatment and at the end of treatment.

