### **13.3.3 Analysis of Vital Signs**

Each vital sign (temperature, blood pressure (systolic and diastolic), respiration rate, and heart rate) and respective change from baseline will be summarized and presented by treatment arm and study visit. Patients with clinically significant abnormalities in vital signs as compared to baseline will be listed.

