7.6.2 Laboratory Abnormalities

Only data collected by the central laboratory will be summarized. Local laboratory data collected for the purposes of planning treatment administration, dose modification, or monitoring adverse events, will not be summarized.

Normal ranges will be used to identify values that are outside the normal ranges and abnormal laboratory results will be graded according to the NCI CTCAE Version 4.0.

Descriptive statistics will be provided for selected test results and for the change from baseline by visit.

ARN-509-003 Statistical Analysis Plan v7.0 26 June 2017

Page 18 of 34

A shift summary of baseline grade by maximum post-baseline CTCAE grade will be presented, as appropriate. For each laboratory parameter, the baseline laboratory value will be defined as the last laboratory value collected on or prior to the date of the first dose of study drug. Patients who develop toxicities of Grade \geq 3 will be listed.

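### SAP 7.6.3 summarises vital signs at baseline and afterwards only counts marked abnormalities, in conflict with Protocol 13.3.3, which calls for change from baseline by arm and visit

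*SAP*

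**What the plan says.** Protocol 13.3.3 (Analysis of Vital Signs) covers temperature, systolic and diastolic pressure, respiration rate and heart rate. It says that each sign and its "respective change from baseline will be summarized and presented by treatment arm and study visit", and that patients with clinically significant abnormalities will be listed.

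SAP 7.6.3 (Vital Signs) names the same five signs but says that each "at baseline will be summarized and presented by treatment group". Its post-baseline output is one sentence: "The number and percentage of subjects with marked abnormalities in vital signs as compared to baseline will be summarized and listed". The criteria that follow have two parts each. The upper criterion for systolic pressure is "Absolute result > 160 mmHg and increase from baseline > 20 mmHg" and for diastolic pressure "Absolute result > 100 mmHg and increase from baseline > 10 mmHg". The lower limits and the heart-rate limits are built in the same way. Temperature and respiration rate have no criterion.

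The data for a by-visit summary will exist. Protocol 7.1.4 says of the vital-signs measurements, temperature and respiratory rate included, that they "will be performed after resting for 5 minutes at Screening and every scheduled visit during treatment and at the end of treatment".

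The neighbouring laboratory section, SAP 7.6.2, does keep this kind of summary: "Descriptive statistics will be provided for selected test results and for the change from baseline by visit".

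**The concern.** A programmer who works from SAP 7.6.3 would produce a baseline table, a marked-abnormality table and a listing. The table that the protocol promises would not be made. Three things follow.

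- No vital-signs output would show whether mean blood pressure or heart rate moved differently in the two arms. That is a safety statement the trial has the data to make.
- Temperature and respiratory rate are measured at every scheduled treatment visit but have no specified summary after baseline.
- The remaining output is a count of subjects. If a subject counts once for any qualifying visit, the count depends on how many visits he has. Treatment continues until centrally confirmed metastasis or unacceptable toxicity (Protocol 3.1), and the design assumes that apalutamide delays metastasis (median MFS 25 to 36 months, SAP 4). Time on treatment may therefore differ between arms by design, and an imbalance in the count can arise from exposure alone.

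**Working it through.** **Step 1. The two texts side by side.** Neither document gives a sample size, test or power for vital signs, so there is no stated figure to reproduce.

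| Item | Protocol 13.3.3 | SAP 7.6.3 |
|---|---|---|
| Values at baseline, by arm | yes | yes |
| Values after baseline, by arm and visit | yes | no |
| Change from baseline, by arm and visit | yes | no |
| Abnormalities listed | yes | yes |
| Abnormalities counted, explicit criteria | no | yes, for systolic, diastolic and heart rate |
| Temperature and respiration rate after baseline | yes | nothing specified |

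No other section of the main SAP restores the second and third rows.

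**Step 2. Why the count grows with exposure.** The SAP counts subjects, and its natural reading is any post-baseline visit. A subject with k visits is flagged if at least one visit qualifies. Adding a visit can add a flag but never remove one, so the probability of a flag cannot fall as k rises. This needs no assumption about blood pressure.

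**Step 3. Size of that effect with no drug effect.** Inputs:

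- From the documents: the systolic criterion above (over 160 mmHg and a rise of more than 20 mmHg), and an entry limit below 160 mmHg (Protocol 4.2, which adds "Patients with a history of uncontrolled hypertension are allowed provided blood pressure is controlled by anti-hypertensive treatment").
- Assumed: true systolic mean 135 mmHg, between-patient SD 12, visit-to-visit SD s of 8 or 12, independent visit errors, and 8 visits in one arm against 12 in the other.

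Model: baseline B = T + e0 with B < 160, and visit v gives Y(v) = T + e(v), where T is normal with mean 135 and SD 12 and each e is normal with mean 0 and SD s. A subject is flagged if, at any v from 1 to k, Y(v) > 160 and Y(v) − B > 20. Shares by simulation:

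| Visit SD | k = 8 | k = 12 | Difference |
|---|---|---|---|
| 8 | 4.2% | 5.6% | 5.6 − 4.2 = 1.4 points |
| 12 | 16.4% | 21.2% | 21.2 − 16.4 = 4.8 points |

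The arms are identical in blood pressure, so the whole difference comes from exposure. A repeat of the simulation gave the same shares to within 0.1 point.

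**Step 4. Where 8 and 12 fall in the schedule.** Under Protocol 8.4 the post-baseline visits are Cycles 2 to 6 (five), then 7, 9, 11 and 13 (nine in all), then 17, 21 and 25 (twelve). So 8 visits reach Cycle 11 and 12 visits reach Cycle 25. The 12:8 ratio of 1.5 is illustrative. A smaller ratio would give a smaller difference.

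**The case against.** **A reader might infer that the threshold counts would hide a blood-pressure effect.** The documents do not support this. It would follow from judging the count at one visit, but the SAP counts subjects, most naturally over all visits. On the Step 3 assumptions, with ten visits in each arm, a true rise of 5 mmHg moves the flagged share from 5.0–18.9% to 13.2–32.1% (the ranges span visit SD 8 to 12). With 800 against 400 patients that gives over 99% power at two-sided 0.05, and a 3 mmHg rise about 76–86%. A set of runs on other assumed inputs gave 93–100% and 53–80%. Power is in any case only a yardstick here, because both documents treat vital signs descriptively. A large sustained shift would probably show.

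**A reader might also infer that the counts are the only place where a shift could appear.** They are not. SAP 7.6.1 tabulates adverse events by preferred term and grade, so reported blood-pressure rises would appear there, and the IDMC sees unblinded safety data (SAP 6). The QT sub-study SAP (5.2) analyses change in heart rate, though in only about 17 subjects. None of these is a mean-change table for blood pressure in the main trial.

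**A reader might infer that the table was deleted from an earlier SAP.** This cannot be shown. Earlier SAP text is not available, and the SAP change log lists major changes only, so its silence proves little.

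**The SAP is written as a supplement to the protocol (SAP 1) and does not expressly withdraw 13.3.3.** This is fair, and the SAP also adds explicit criteria and percentages that the protocol lacks. But 7.6.3 specifies the same summary for the same five signs with different content, and a reader cannot tell which will be produced.

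**The last sentence of 7.6.3 introduces categories that do not follow it.** It probably leads into the criteria table, displaced when the PDF was read. Lost text cannot be fully excluded.

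**Conclusion.** The conflict stands on the text alone. Protocol 13.3.3 calls for values and change from baseline by arm and visit, and SAP 7.6.3 gives baseline values and abnormality counts. As written, no vital-signs table shows a mean shift, and temperature and respiration rate have no specified post-baseline summary.

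The exposure effect on an all-visit count is certain in direction. Its size, 1.4 to 4.8 percentage points in the illustration, rests on assumed blood-pressure values, independent visit errors and 8 against 12 visits, none of which is a document figure except the entry limit and the criterion. A by-visit change table is much less affected, though late visits still describe only those who remain on treatment.

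The point is minor. Vital-signs analyses are descriptive, and no efficacy result, eligibility rule or trial conduct depends on them. It is a matter of complete and interpretable safety reporting, not of a hidden harm.

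**What to change.** In SAP 7.6.3, restore descriptive statistics for each of the five vital signs and for its change from baseline, by treatment group and scheduled visit. Keep the marked-abnormality table alongside, and say whether a subject is counted over all post-baseline visits. If the sponsor prefers not to produce the by-visit summary, the SAP should record the departure from Protocol 13.3.3 with a reason and state how temperature and respiration rate are reported after baseline.

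The cost is one extra standard table from data already collected. Alpha, sample size and trial conduct do not change.

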7.7 OTHER EVALUATIONS

7.7.1 Second Progression-Free Survival (PFS2)

PFS2 is defined as the time from randomization to second documentation of investigatorassessed disease progression (PSA, radiographic, symptomatic, or any combination) or death (any cause) on subsequent treatment (whichever occurs first) + 1 day. Subjects without a documented progression will be censored at the last date known to be progression-free or death whichever occur first.

PFS2 will be analyzed using time-to-event analysis methods outlined in section 7.5.

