	
Rationale: The previous patient-reported outcomes analysis incorporated a 16-point improvement in the Functional Assessment of Cancer Therapy-Prostate (FACT-P) total score as the definition for a health-related quality of life improvement. Improvement of the total score is not applicable for this study population. The magnitude of a clinically meaningful change was redefined.

13.4.2 Health-Related Quality of Life and Prostate Cancer-Specific Symptoms Analysis	A 10-point change in the FACT-P total score is considered clinically meaningful. Therefore, any patient experiencing a 10-point decrement in FACT-P total scores from baseline will be considered to have experienced clinically meaningful deterioration in functional status.
	
Rationale: The completion of the PRO questionnaires was reduced after Cycle 13 to every other cycle to relieve the burden to the patient and for consistency with other Sponsor protocols.

7.4 Patient-Reported Outcomes; 8.3 Day 1 of Cycles n...; Appendix 1, Footnote 18	Reduced the collection of FACT-P and EQ-5D questionnaires after Cycle 13 to every other cycle.
	
Rationale: Added second progression-free survival (PFS2) as an evaluation per agreement with health authorities.

Synopsis, Other Evaluations; 3.2.3 Other Evaluations; 8.8 Survival Follow-Up; 13.4.1 Second progression-free survival (PFS2); Appendix 1	This endpoint is defined as the time from randomization to second documentation (progression on first subsequent therapy) investigator-assessed disease progression (PSA, radiographic, symptomatic, or any combination) or death from any cause.
	
Rationale: Inclusion criterion was modified for consistency with Section 5.1 of the protocol and based on Investigator feedback.

4.1 Inclusion Criteria, Criterion #1	Clarified determination of PSADT
	
Rationale: Inclusion of patients with documented Gilbert's disease is allowed

4.1 Inclusion Criteria, Criterion #11	Added exception to elevated bilirubin in cases of documented Gilbert's disease.
	
Rationale: Bone sparing therapies indicated for the treatment of skeletal events due to bone metastases are not allowed as concurrent therapy.

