#### **8.9 LONG-TERM FOLLOW-UP**

- Obtain survival status, recording of development of symptomatic progression, initiation of any new systemic anti-cancer therapies, progression on first subsequent therapy (PFS2), and MRU every 4 months via clinic visit, telephone contact, or an alternative contact method per institution policy/practice. The FACT-P and EQ-5D questionnaires will be collected up to 12 months post-progression.
- **In addition, if patients discontinue study treatment prior to documented disease progression (ie, distant metastasis, see Section 7.1.8),** obtain CT of the chest, abdomen, and pelvis, plus bone scan and submit for BICR to evaluate for disease progression (every 16 weeks, until documentation of disease progression)

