## 13.4 OTHER EVALUATIONS

### 13.4.1 Second Progression-free Survival (PFS2)

This endpoint is defined as the time from randomization to second documentation of investigator-assessed disease progression (PSA, radiographic, symptomatic, or any combination) or death from any cause.

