
13. Tumor Imaging: CT scans of chest, abdomen, and pelvis plus bone scan will be performed at Screening (scans obtained prior to signing informed consent will be allowed provided the timing of the scans fall within the Screening window). Scans must be submitted for BICR to confirm patient eligibility. During treatment, CT scans of chest, abdomen and pelvis plus bone scan will be performed to assess disease status every 16 weeks (<math>\pm 7</math> days) from Cycle 1 Day 1, or whenever disease progression is suspected, and at the end of treatment. Note that tumor imaging should continue on this calendar schedule regardless of any delays in dosing. Patients who have a contraindication to IV contrast may have MRI exams of the brain, abdomen, and pelvis performed in lieu of CTs and a non-contrast CT of the chest. All scans will be submitted for blinded independent central review to confirm patient eligibility and assess for disease progression on study. Subjects who discontinue treatment before documented disease progression should continue with disease assessments during Long-term Follow-up every 16 weeks (<math>\pm 7</math> days) until disease progression (see also Footnote 4). For all subjects, at the time of unblinding and crossover, radiographic scans will no longer be to be submitted for blinded central independent review. Subjects will be followed for progression per Investigator decision including symptoms, radiographic scans or PSA.

14. Progression on First Subsequent Therapy: The date of progression on first subsequent therapy as assessed by the investigator and method of assessment of disease progression (radiographic, PSA, or both) will be collected.

15. Physical Examination: At Screening, a complete physical examination of major body systems, including known and suspected sites of disease, should be performed. During subsequent visits, either a full or abbreviated physical exam will be performed. New abnormal physical exam findings must be documented and followed by a physician or other qualified staff at the next scheduled visit. Height will be recorded at Screening only. Body weight will be recorded at Screening and at every scheduled visit during treatment and at the end of treatment.

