7.5.2 Primary Endpoint (MFS)

The primary efficacy endpoint is metastasis-free survival (MFS), defined as the time from randomization to first evidence of BICR-confirmed radiographically detectable bone or soft tissue distant metastasis (simply referred to as "metastasis" from this point forward) or death due to any cause (whichever occurs earlier) + 1 day.

ARN-509-	-003					
Statistical	Analysis	Plan	v7.0	26.	June	2017

Page 11 of 34

MFS data for patients without metastasis or death will be censored on the date of the last tumor assessment (or, if no tumor assessment was performed after the baseline visit, at the date of randomization + 1 day).

Additional censoring rules will vary according to whether the analysis is performed for US or ex-US regulatory purposes, as follows; both results will be provided in the clinical study report.

Scenario	US regulatory guidance	ex-US regulatory guidance ⁴
Data from patients who are lost to follow-up or whose disease progression (development of metastasis) or death occurs after 2 or more consecutively missing or unevaluable tumor assessments	Censored on the date of the last tumor assessment that the patient was known to be metastasis-free	Time of progression will be determined using the first date when there is documented evidence of progression or death (whichever occurs earlier) regardless of missed or unevaluable tumor assessments
Patients that receive new systemic anti-cancer therapy prior to documented disease progression (development of metastasis) or death	Censored on the date of the last tumor assessment prior to the start of the new systemic anti-cancer therapy	Time of progression will be determined using the first date when there is documented evidence of progression or death (whichever occurs earlier) regardless of change of therapy

Disease progression (development of metastasis) will be assessed by an independent core imaging laboratory using the Response Evaluation Criteria in Solid Tumors (RECIST v1.1).⁵ The appearance of new (or distant) metastatic lesions denotes disease progression. For new bone lesions detected on bone scans, a second imaging modality (e.g., CT or MRI) will be required to confirm progression.

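### SAP 7.7.1 does not count as PFS2 events all the deaths that protocol 13.4.1 counts, and its definition and censoring sentences disagree with each other

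*SAP*

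**What the plan says.** Protocol 13.4.1 measures PFS2 from randomization to a second investigator-assessed progression or death. Its event clause ends "PSA, radiographic, symptomatic, or any combination) or death from any cause". It requires neither an earlier progression nor subsequent treatment before a death counts, and it states no censoring rule.

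SAP 7.7.1 keeps the progression component but gives the death component as "or death (any cause) on subsequent treatment (whichever occurs first) + 1 day". The next sentence is the censoring rule: "Subjects without a documented progression will be censored at the last date known to be progression-free or death whichever occur first". The section then refers to the time-to-event methods of SAP 7.5 (Kaplan-Meier and Cox).

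Three other places bear on the reading:

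- In the protocol's data collection, subsequent therapy qualifies progression and not death. Appendix 1, footnote 14 asks for "The date of progression on first subsequent therapy as assessed by the investigator and method of assessment of disease progression", and section 8.9 lists the same item.
- For MFS, another composite that includes death, SAP 7.5.2 keeps deaths out of the censored group: "MFS data for patients without metastasis or death will be censored on the date of the last tumor assessment".
- PFS2 is listed among the other evaluations (protocol 3.2.3, SAP 2.2) and has no place in the hierarchy of SAP 7.5.3.

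**The concern.** The SAP describes itself as a supplement to the protocol, yet its PFS2 event set is narrower. It places a subsequent-treatment condition on death, and it names death as a possible censoring date. Its two sentences also disagree with each other about some deaths. The censoring sentence does not say whether a documented progression means the first or the second.

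Event status feeds directly into the Kaplan-Meier and Cox estimates. Censoring a death treats that patient as if he remained at the same risk of a later second progression as those still followed, which is informative censoring. PFS2 then looks longer than under the protocol in both arms. The hazard ratio can move either way, depending on how the treatment effect on the lost deaths compares with the effect on the remaining events. Two programmers working from the same text could also derive different event sets.

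**Working it through.** **Step 1: classify deaths under each text.** The SAP definition column takes the subsequent-treatment phrase to qualify death, which is where it is placed.

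| Patient | Protocol 13.4.1 | SAP definition sentence | SAP censoring sentence |
|---|---|---|---|
| Dies, no documented progression, no subsequent treatment | Event | Not an event | Censored |
| Dies on subsequent treatment, no documented progression | Event | Event | Censored |
| Dies on subsequent treatment after a first progression only | Event | Event | Censored if progression means the second; not covered if it means the first |
| Dies after a first progression only, before or off subsequent treatment | Event | Not an event | Censored if progression means the second; no rule if it means the first |

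The protocol column is the same in every row. The SAP conflicts with the protocol in rows 1 and 4 whichever sentence governs. It contradicts itself in row 2. Row 3 turns on an undefined word.

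**Step 2: inputs for a size.** Neither document gives a PFS2 event count, a PFS2 effect size, or a rate of death without progression, so there is no stated figure to reproduce. Assumptions for illustration:

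- Constant cause-specific hazards.
- f = the share of placebo PFS2 events, by the protocol definition, that are deaths lost to censoring. It is unknown and varied from 5% to 30%.
- Hazard ratio for all other PFS2 events: 0.70, borrowed from the MFS planning value in SAP 4.
- Hazard ratio d for the lost deaths: 0.60, 0.75 (the OS planning value in SAP 4) or 1.0.

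**Step 3: formulas.** Let the placebo hazard under the protocol definition be h. After the loss it is (1 − f)h.

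- Placebo median ratio = 1/(1 − f).
- Apalutamide hazard under the protocol = [0.70(1 − f) + f·d]h; after the loss it is 0.70(1 − f)h. Median inflation = f·d / [0.70(1 − f)].
- Hazard ratio under the protocol = 0.70(1 − f) + f·d. With the deaths censored it is 0.70.
- Bias = 0.70 − [0.70(1 − f) + f·d] = f(0.70 − d).

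**Step 4: results.**

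| f | Placebo median | Apalutamide median, d = 0.75 | Protocol HR, d = 0.60 | d = 0.75 | d = 1.0 |
|---|---|---|---|---|---|
| 5% | +5% | +5.6% | 0.695 | 0.7025 | 0.715 |
| 10% | +11% | +11.9% | 0.690 | 0.705 | 0.730 |
| 20% | +25% | +26.8% | 0.680 | 0.710 | 0.760 |
| 30% | +43% | +45.9% | 0.670 | 0.715 | 0.790 |

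Worked at f = 20%, d = 0.75: placebo 1/0.80 = 1.25; apalutamide 0.20 × 0.75 / (0.70 × 0.80) = 0.15/0.56 = 26.8%; protocol HR 0.56 + 0.15 = 0.710 against 0.70.

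At d = 0.75 the bias is −0.05f, so at most 0.015 in size for f up to 30%. At d = 1.0 it is −0.30f: 0.03, 0.06 and 0.09 at f = 10%, 20% and 30%, in favour of apalutamide. At d = 0.60 it runs the other way, 0.01 to 0.03 over the same range of f.

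**The case against.** The best defence is that the censoring clause does no work. A last date known to be progression-free cannot fall after death, so taking the earlier of the two never changes the date. On that view the sentence is loose shorthand for patients without the event just defined, and only the placement of a phrase is left. The first part is sound: naming death does not alter any censoring date, and the text shows ambiguity more than a settled rule that all deaths are censored. But this reading recovers only deaths on subsequent treatment. Deaths before or off it remain outside the definition sentence. To recover the protocol endpoint one must also set aside the subsequent-treatment phrase as it applies to death, and a programmer should not have to do that.

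The narrowing may have been intended. The SAP's summary of changes says PFS2 was added by agreement with health authorities, and that agreement is not in the documents. The summary's silence on any narrowing proves little, because it lists major changes only and the definition entered when PFS2 was added. Intent therefore stays open, but the two documents still disagree.

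Two stronger inferences should be resisted:

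- A reader might take the SAP 7.5.2 rule headed "Patients that receive new systemic anti-cancer therapy prior to documented disease progression (development of metastasis) or death" as proof that the SAP expects patients to start subsequent treatment with no PFS2 progression. That rule concerns centrally reviewed distant metastasis. PFS2 progression is judged by the investigator and may rest on PSA or symptoms, so such a patient may already have a progression for PFS2.
- A reader might try to sharpen the size with a two-stage model that uses the 25-month planning median for first progression. That is an MFS median and already counts deaths, so a separate death hazard would count them twice. The documents also give no time from first to second progression.

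**Conclusion.** The conflict is real and should be corrected. As written, SAP 7.7.1 does not deliver the protocol's PFS2 endpoint under the literal reading or under the reading in which its definition sentence governs, and it treats some deaths in two ways.

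The direction for the medians is clear: PFS2 is overstated in both arms. The size is not known. The figures above depend on constant hazards, a hazard ratio of 0.70 borrowed from MFS, and a lost share f that the documents do not supply. Within that illustration the effect on the medians can be material. The effect on the hazard ratio is small if the death effect is close to the effect on other events, and larger if treatment has little effect on death.

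The documents do not support reading this as a threat to the trial's main conclusions. PFS2 carries no allocated alpha and no power claim. MFS has its own event and censoring rules, and OS counts every death.

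**What to change.** Reconcile SAP 7.7.1 with protocol 13.4.1 by rewriting two sentences:

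- **Event:** second investigator-assessed progression or death from any cause, whichever is first. Attach any subsequent-therapy qualifier to progression only, as in the protocol's data collection.
- **Censoring:** only patients alive without second progression, at the last date known to be alive and free of second progression. Say second explicitly.

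If a narrower death component was agreed with health authorities, amend protocol 13.4.1 to match, and still remove death as a censoring date for deaths that count as events.

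The cost is two sentences in the SAP, or a short protocol amendment in the second case. No new data are needed: protocol 8.9 and Appendix 1, footnote 4 already collect survival status and progression on first subsequent therapy every 4 months.
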